6.1.2 SCREENING VISIT

Participants will be screened for the study only after signing an approved Informed Consent Form. Screening data will be collected as per the Schedule of Events (Table 1) for the screening visit and ongoing visits. Patients can be re-screened at the principal investigator's discretion.

6.1.3 BASELINE VISIT

Eligibility criteria will be confirmed at the Baseline visit (Week 0). Laboratory results must be reviewed by a physician prior to randomisation. Study medication should be dispensed on the day of randomisation. Baseline data will be collected as per the Schedule of Events (Table 1).

6.1.4 WEEK 2, 6, 8, 15, 17, 28, 30, 41, 43 SAFETY VISITS

For additional drug-specific safety visit requirements please see the individual drug appendices.

6.1.5 MONTH 1, 3, 6, 9 VISITS

Follow up data will be collected as per the Schedule of Events (Table 1) for the relevant quarterly visits. At each follow up timepoint, a status form is completed; in the event of a missed visit, the status form must be completed.

6.1.6 MONTH 12 OR END-OF-STUDY VISIT

Month 12 data will be collected as per the Schedule of Events (Table 1) above for the month 12 visit and ongoing section. In the event a participant wishes to stop study medication and withdraw from further data collection, a withdrawal form must be completed (see section 5.5). Where possible a withdrawal visit should be scheduled to collect unused medication and undertake a final set of outcome assessments. In cases where the participant completes the study to month 12, a withdrawal form should be completed at the final visit to indicate the participant did not withdraw.

6.2 DATA ENTRY

6.2.1 RANDOMISATION

Randomisation of participants will be undertaken as per the instructions in the Randomisation User Guide provided separately.

6.2.2 MACRO ECRF

Authorised staff at sites will transcribe baseline and follow up participant data directly from the participants medical records or from source data into the study eCRF by going to www.ctu.co.uk and clicking the link to access MACRO. A full audit trail of data entry and any subsequent changes to entered data will be automatically date and time stamped, alongside information about the user making the entry/changes within the system.

Study site staff will be delegated by the site PI to access the eCRF and randomisation systems via a Study Site Delegation Log. The request for user access must go to the Trial Manager, who will submit user requests for all sites to the KCTU team upon receipt of completed Study Site Delegation Logs. Requests for user access will be processed within a maximum of 5 working days.

Training videos for data entry staff, study site monitors and trial managers / trial co-ordinators are available at www.ctu.co.uk under the 'Training' section. Users can self-register and should select the MACRO related training videos.

6.2.3 PATIENT ONLINE DATA ENTRY (DRDOCTOR)

Data will be entered directly from the patient onto a secure online platform (DrDoctor). Site staff and monitors will be able to check if data has been entered and view the data only. Training for patients and site staff regarding the remote data capture platform (DrDoctor) will be provided.

6.2.4 SAMPLE DATA ENTRY (CAPTURE)

Clinical and sample data will be entered onto a secure web-based forms system used to capture clinical research data for use in research studies and clinical trials 'CAPTURE' (ChArting PaTient outcomes Using an online REsource). CAPTURE has been developed by the NIHR Biomedical Research Centre at Guy's and St Thomas' NHS Trust (GSTT) and King's College London (KCL). Participants will not have access to the CAPTURE system. Data will be entered directly by the site staff and the CAPTURE team. Users will be added/managed by the CAPTURE team.

6.2.5 SKIN PHOTOGRAPHY DATA ENTRY

Standardised photographs of participants' skin will be taken by appropriately trained site staff and uploaded by staff to a secure web-based database hosted on a secure server managed by GSTT. Participants will not have access to the web-based database on which photographs are stored.

6.3 **PRE-RANDOMISATION DATA COLLECTION**

6.3.1 REGISTRATION

When the participant has signed consent, the study site staff should register the participant in the MACRO eCRF system. Upon registration, the system will assign a unique study PIN to be used for the participant throughout the study.

6.3.2 ELIGIBILITY

All eligibility checks must be completed and a physician must confirm eligibility prior to randomisation.

6.3.3 MEDICAL HISTORY

Relevant medical history must be recorded including:

- Date of onset
- Co-morbidities/ past medical history
 - including history of:
 - atopic conditions such as asthma, allergic rhinoconjunctivitis (hay fever), atopic eye disease, eosinophilic oesophagitis, food allergy
 - other eye disorders (including dry eye, conjunctivitis, keratitis, blepharitis, , previous ocular surgery, contact lens wear)
 - skin infections (bacterial and viral including herpes simplex virus and shingles)
 - pain in and around joints
 - acne requiring systemic treatment (e.g. antibiotics/ isotretinoin)
 - o diagnosis, date of onset, active or in remission
- Treatment history for eczema (topical/ phototherapy/ systemic therapy)
- Current eczema treatment
 - o start date, effect
- Concomitant medications
 - If the participant is taking any medications at baseline, the relevant condition should be recorded in the medical history.
- Smoking history
- Alcohol consumption
- Conception/ pregnancy plans (men and women, relevant to men in case of methotrexate)

6.3.4 DEMOGRAPHICS

Relevant demographic information will be collected prior to randomisation including initals, age (date of birth), sex at birth, ethnicity, weight, and height.

6.3.5 SKIN EXAMINATION

This will cover:

- Skin type (type I-VI)
- Flexural eczema (and sites)
- Non-flexural eczema (and sites)
- Presence of head and neck eczema/ exposed site eczema
- Vesicular hand eczema
- Discoid eczema
- Nodules
- Follicular eczema
- Ichthyosis
- Keratosis pilaris
- Palmar hyperlinearity
- Erythroderma
- Acne

- Eye signs
- 6.3.6 METHOD OF PARTICIPANT IDENTIFICATION

The method of participant identification (for example, referred to the trial by a clinician, self-referred via the trial website) will be assessed at screening. Furthermore, for patients self-referring via the website, the route through which they identified the trial and self-referral pathway will be explored (for example, social media, NIHR newsletters, poster advertising).

6.3.7 RANDOMISATION

Sites must confirm in the eCRF system whether participants were randomised into the study or not. The randomisation procedure and access to the randomisation system is described in the Randomisation User Guide provided separately.

6.4 **EFFECTIVENESS**

The core outcome set for eczema recommended by the Harmonising Outcome Measures for Eczema (HOME) initiative (http://www.homeforeczema.org/) is included in this trial.

6.4.1 OBJECTIVE MEASURES (BLINDED ASSESSOR)

6.4.1.1 ECZEMA AREA AND SEVERITY INDEX (EASI)

The EASI is an objective disease severity score that assesses clinical signs in eczema across four body sites (arms, face/neck, trunk, legs) including erythema, induration, excoriation, lichenification (each on a 4 point scale) as well as area of involvement, with a maximum score of 72. This will be assessed by a nominated blinded-assessor at site. Site staff will only be delegated to complete this assessment if they have completed the relevant training and are certified to complete the assessments. If the investigator feels that there is a temporary confounding skin condition that will significantly affect the ability to obtain an accurate EASI (e.g. severe sunburn) then they should defer the visit / blinded assessment as appropriate, within the visit window where at all possible (see section 6.1.1).

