the comparative effectiveness of systemic therapies is lacking and that "larger, clearly reported, clinically relevant studies are needed to properly compare the benefits of these drugs in adults and children with severe eczema"5. Dupilumab was the first licensed targeted (biologic) therapy for eczema and has a strong evidence base versus placebo but has never been compared with standard systemic therapy^{8,9}. Likewise for the even newer agents tralokinumab, lebrikizumab and JAK inhibitors (abrocitinib, upadacitinib and baricitinib), there is a strong evidence base versus placebo^{10,11}, but there has been no comparison versus standard systemic therapy. There is also minimal available head to head data between the novel agents. Industry led head to head trials have been conducted between JAK inhibitors and dupilumab^{12,13} however the early primary endpoints (as early as 2 weeks) are not optimal given that dupilumab can take 6 months to achieve maximum benefit⁹. A recent network meta-analysis suggested that there is an absence of well powered headto-head trials, that dupilumab and ciclosporin may have better short term effectiveness than methotrexate and that "studies directly comparing established and novel treatments beyond 16 weeks are needed"¹³. Another recent systematic review states "to more directly compare medication efficacy, a standardised controlled trial comparing biologic and non-biologic systemic therapies is needed"14.

Outwith efficacy and effectiveness, the standard and novel systemic therapies confer very different side effect profiles. Whilst the side effects of ciclosporin and methotrexate are well established, those of the more novel agents are less so and of those that we now know about, many were unexpected. Side effects on dupilumab such as ocular surface disease, facial flares and arthritis can affect tolerability for patients. Likewise on JAK inhibitors, infections (including herpes simplex and varicella zoster), acne, blood derangement and rarely venous thrombo-embolism impact patients. Safety is therefore a focus of increasing attention for those prescribing systemic therapies in this context and any informative head-to-head comparative data of the key agents if of clinical utility.

1.1.2 THE COST-EFFECTIVENESS OF SYSTEMIC TREATMENTS USED TO TREAT MODERATE-SEVERE ECZEMA IN ADULTS

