6.1.1 VISIT WINDOWS

The screening visit can be scheduled up to 12 weeks prior to randomisation. Main trial visits are scheduled at month 1 post-randomisation and then months 3,6,9,12, with a visit window of 7 days either side (likewise for PROM data capture). In the event that a visit falls outside the target visit window of +/- 7 days, the visit should be scheduled as soon as possible and the data should be entered into the intended visit. Subsequent visits should be scheduled as per the original visit schedule. Please ensure the month 6 visit (primary endpoint) falls within the visit window where at all possible. A timepoint is considered missed if the visit is not conducted by the start of the subsequent visit window.

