8.4 BLINDING STATUS OF RESEARCHERS*

TABLE 2 BLINDING STATUS

Individual blinding status	Blinded	Unblinded
Chief Investigator		Х
Academic Lead		Х
Principal Investigators and all other staff at site		Х
Trial Manager/Trial Co-ordinators		Х
Senior Statistician	X	
Junior Statistician		Х
Pharmacists at site		Х
Trial Pharmacist		Х
Trial Participants		Х
EASI and IGA outcome assessors	X	
Local research teams (excluding outcome assessors)		Х
Treating Clinicians		Х
Sponsor (CRA/Monitor)		Х
Trial Steering Committee (TSC)	X	
Data Monitoring Committee (DMC)		Х

*For roles not listed please refer to study delegation logs

The blinding status of the research team with respect to an individual patient's allocation is detailed in Table 2 above.

Only the Junior Trial Statistician will see summary data split by intervention allocation, as this is required for the preparation of reports to the DMEC. No other members of the trial team will have access to this information until the primary analysis is complete. This information will be available to the DMEC members in closed reports.

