10.2 ADVERSE EVENTS OF SPECIAL INTEREST (AESI)

The AESI listed below will be recorded in more detail via AESI report forms throughout the trial. A template document outlining the information to be recorded will be provided to sites, to be recorded onto Source Data Worksheets or directly into the participants medical records for transcribing into the MACRO eCRF system:

- Ocular surface disease e.g. conjunctivitis/ blepharitis/ keratitis/ dry eye/ keratoconus
- Pain in or around joints
- Facial skin rashes (including acne)

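### An unblinded investigator may postpone the blinded month-6 EASI, so the timing of the primary measurement, though not its scoring, is open to knowledge of the arm

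*Protocol*

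**What the plan says.** Section 6.4.1.1 has EASI scored by a trained, certified, blinded assessor at site. It then adds a deferral rule: "If the investigator feels that there is a temporary confounding skin condition that will significantly affect the ability to obtain an accurate EASI", "then they should defer the visit / blinded assessment as appropriate, within the visit window where at all possible". The only example is severe sunburn. There is no list of conditions, no written criterion beyond the condition being temporary and materially affecting the score, and no confirmation by someone blinded.

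Table 2 in section 8.4 puts "Principal Investigators and all other staff at site" in the unblinded column. At site, only the "EASI and IGA outcome assessors" are blinded.

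Section 6.1.1 sets a window of 7 days either side. For a visit outside it, "the visit should be scheduled as soon as possible and the data should be entered into the intended visit". The outer limit is that "A timepoint is considered missed if the visit is not conducted by the start of the subsequent visit window". The same section asks that month 6 be kept in window, but only where that can be managed.

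On skin events, section 1.1.1 says "Side effects on dupilumab such as ocular surface disease, facial flares and arthritis can affect tolerability for patients", and section 10.2 lists "Facial skin rashes (including acne") as adverse events of special interest.

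**The concern.** The trial is open to participants and site staff. Its protection against assessment bias is that the primary score comes from someone who does not know the allocation. That protection covers how the skin is scored on the day. It does not cover a decision by someone else, who knows the drug, that this is not the day to score it.

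If that decision is influenced by the arm, or by an opinion on whether a rash is a drug effect, the month-6 values in one arm could be taken at systematically different moments of the disease course than in another. A later analysis cannot recover the score that would have been given on the original date. Who may postpone the assessment is a matter of trial conduct that the protocol itself fixes, so it is not something merely left to an analysis plan.

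**Working it through.** **1. Who decides.** Section 6.4.1.1 names the investigator as the decider and, in the same paragraph, treats the blinded assessor as a different person. Table 2 confirms that the first is unblinded and the second blinded.

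**2. How late a value can be.** Month 6 is week 26 and month 9 is week 39 (Table 1). The month-9 window opens at week 39 − 1 = week 38. The outermost delay is 38 − 26 = 12 weeks, or 11 weeks beyond the +7-day limit. This is the general bound for any late visit; the protocol does not grant it specifically for deferral.

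**3. Whether possible triggers differ by arm.** The appendices list:
- ciclosporin: skin reactions (common);
- methotrexate: skin reactions (common), photosensitivity (uncommon);
- dupilumab: facial rash (uncommon);
- abrocitinib: acne, and herpes simplex including eczema herpeticum (common).

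The types differ, but every arm, including the control, has some. Face/neck is one of the four EASI sites and erythema is a scored sign, so a facial eruption is a plausible candidate for deferral. The protocol does not say that it is one.

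**4. The switch at month 6.** Section 2 defines response as EASI50 together with a DLQI fall of at least 4. Failing the DLQI part alone therefore makes a participant a non-responder. Table 1 places EASI, switch review and dispensing at week 26. Section 6.4.1.1 allows the blinded assessment alone to be deferred. No text says whether the switch then waits for the EASI, so a value filed as month 6 could have been taken on the second drug.

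**5. Scale.** First, the plan's own sample size, from section 12.1 (difference 6.6, SD 13.6, 90% power, 20% loss) and section 12.5.1 (two-sided 0.025):

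n = 2 × (2.2414 + 1.2816)² × 13.6² / 6.6² = 105.4, so 106 evaluable per arm; 106 / 0.8 = 132.5, so 133. With the t distribution, 107 evaluable give 90.1% power and 107 / 0.8 = 133.75, so 134. The stated 134 is reproduced.

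The standard error of the difference is 13.6 × √(2/107) = 1.86. Let b = (excess share deferred in one arm) × (mean EASI shift per deferral). Then:
- type I error = Φ(−2.2414 + b/1.86) + Φ(−2.2414 − b/1.86);
- power, if b is towards the null = Φ((6.6 − b)/1.86 − 2.2414), which is 90.5% at b = 0.

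The protocol gives no deferral rate and no shift. Both columns on the left are assumptions.

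| Excess deferred | Shift (points) | b (points) | b / 6.6 | Type I error | Power if towards null |
|---|---|---|---|---|---|
| 2% | 2 | 0.04 | 0.6% | 0.025 | 90% |
| 5% | 5 | 0.25 | 3.8% | 0.026 | 88% |
| 10% | 5 | 0.5 | 7.6% | 0.030 | 85% |
| 10% | 10 | 1.0 | 15% | 0.047 | 78% |
| 20% | 10 | 2.0 | 30% | 0.12 | 59% |

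The last row is an extreme. A shift of 10 points per deferral exceeds the 6.6 points that the protocol takes as the minimum clinically important difference.

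**The case against.** A sponsor could fairly say the following.

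- **Scoring is never unblinded.** The assessor remains blinded and certified whatever the date. This stands. A reader might infer that assessor blinding is bypassed; the protocol does not support that, because only the timing, and at worst whether a value is obtained, is exposed.
- **Drug reactions are not named as confounders.** Sunburn is the only example, and the condition must be temporary and matter for the score. This also stands. The link to acne, facial rash or herpes is an inference from the side-effect lists.
- **No arm is shown to benefit.** It is tempting to read the rule as favouring dupilumab or abrocitinib. All four arms list skin effects, and no deferral frequencies are given, so neither unequal frequency nor direction is established.
- **Twelve weeks is a worst case.** The text asks for an in-window assessment where possible and otherwise the earliest one. True, but these are requests; no firmer limit applies to month 6.
- **The switch scenario needs several conditions at once:** the EASI alone deferred, a DLQI failure, and a switch without waiting. Deferring the whole visit would ordinarily move the review with it. Nothing suggests the scenario is common, but nothing excludes it.
- **Some of the information is collected already.** Adverse events carry start and end dates, and facial rashes are recorded in detail. The eCRF and the analysis plan are not shown, so the absence of a deferral field or a sensitivity analysis cannot be asserted.

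What remains is the stated rule itself: an unblinded person decides, on opinion, when the primary outcome is measured.

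**Conclusion.** The point holds in a limited form. Sections 6.4.1.1, 6.1.1 and 8.4 together leave the timing of the blinded primary EASI to a judgement that can be made with knowledge of the arm, with a soft time limit and an unclear relation to the month-6 switch.

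The size and direction of any bias cannot be derived from the protocol. On the assumed range it runs from 0.04 to 2.0 EASI points and is most plausibly well below 1 point. It becomes material only if deferral is both frequent and very unequal between arms. The case for changing the rule rests on the low cost of closing the gap; a large expected distortion has not been shown.

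**What to change.** In section 6.4.1.1, state that the blinded assessor, unaware of allocation, decides on deferral before scoring. The written criteria should turn on whether the eczema signs can be scored, and not on suspected drug cause. A blinded assessor cannot reliably judge drug cause and would be invited to guess the arm.

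Record in the eCRF that the assessment was deferred, the reason, and the actual EASI date. Report deferrals by arm, and repeat the primary analysis without deferred or out-of-window values; the analysis plan is the natural place for this if it is not already there.

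Reconcile sections 6.4.1.1 and 6.1.1 with the month-6 switch review, so that it is clear whether a deferred month-6 EASI can fall after a switch, and flag any such value. Which clinical rule applies is for the trial team to settle.

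The cost is a few lines of protocol and assessor-training wording and a small eCRF addition. The change removes the route through knowledge of the arm; it does not remove real differences between arms in how often skin events occur, which is why deferrals should also be reported by arm.

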6.4.1.2 INVESTIGATOR GLOBAL ASSESSMENT (VIGA-AD)

The IGA is an objective global disease severity measure (validated Investigator Global Assessment scale vIGA-AD, 5-point scale - clear/ almost clear/ mild/ moderate/ severe). This will be assessed by a nominated blinded-assessor at site.

6.4.2 PATIENT-REPORTED OUTCOME MEASURES (PROMS)

Participants should be informed to complete self report measures in the absence of any caregiver prior to each visit as instructed, and will input directly into DrDoctor using a phone, laptop or tablet.

6.4.2.1 PATIENT ORIENTARED ECZEMA MEASURE (POEM)

The POEM is a patient-assessed 7-point instrument to measure patient-reported symptoms including itch, sleep, bleeding, weeping, cracking, flaking and dryness (scored 0-4) with a maximum score of 28.

6.4.2.2 PEAK PRURITIS NUMERICAL RATING SCALE (PPNRS/NRS11)

The PPNRS is a single item, patient assessed measure of peak pruritis, or worst itch, over the previous 24 hours (numerical scale of 0-10).

BEACON

6.4.2.3 RECAP

RECAP is a 7-item patient assessed quiestionnaire to measure AD control. Domains include general perception of eczema, itching, intense itching, sleep disturbance, impact on activities, feelings and acceptibility (each scored 0-4, maximum score 28)

6.4.2.4 PATIENT GLOBAL ASSESSMENT (PTGA)

The PtGA is a patient assessed global measure of their eczema (5 point scale, clear/ almost clear/ mild/ moderate/ severe).

6.4.2.5 DERMATOLOGY LIFE QUALITY INDEX (DLQI)

The DLQI is a 10-point (each scored 0-3) patient assessed measure to determine how much a participants skin condition is affecting their life, encompassing symptoms, embarrassment, daily activities, clothes, sport, work, relationships, sexual activities and burden.

6.4.2.6 PATIENT HEALTH QUESTIONNAIRE-9 (PHQ-9)

The PHQ-9 is a patient assessed 9 question (each scored 0-3) instrument to screen, diagnose and measure the severity of depression. It incoroprates pleasure from activities, feeling low or hopeless, sleep patterns, energy levels, eating habits, self-perception, concentration, speed of talking and moving and thoughts of self-harm or suicide.

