4.2 SECONDARY OUTCOMES

- 1. Eczema severity measured by:
 - a. EASI (blinded assessment)
 - i. EASI50/ EASI75/ EASI90/ EASI100/ absolute EASI ≤ 7 (months 1,3,6,9,12, presented as proportion achieving these outcomes)
 - ii. Change from baseline in EASI (months 1,3,9,12, presented as mean absolute change)
 - b. Investigator Global Assessment²⁵ (vIGA-AD, blinded assessment, months 1,3,6,9,12, proportion clear/ almost clear)
- 2. Patient reported symptoms (months 1,3,6,9,12) measured by:
 - a. Patient Orientated Eczema Measure²⁶ (POEM, mean absolute change from baseline)
 - b. 11 point peak pruritus numerical rating scale²⁷ (NRS, mean absolute change from baseline)
 - c. Overall disease control²⁸ (RECAP, mean absolute change from baseline)
 - d. Patient global assessment (PtGA (5-point scale), proportion clear/ almost clear)
- 3. Quality of life measured by:
 - a. Dermatology Life Quality Index²⁹ (DLQI, months 1,3,6,9,12, mean absolute change from baseline and proportion achieving DLQI ≤ 5)
- Depression and anxiety measured by Patient Health Questionnaire 9-item³⁰ and Generalised Anxiety Disorder 7-item³¹ (PHQ-9 and GAD-7, months 6,12, mean absolute change from baseline and proportion with score < 5)
- 5. Health economic outcomes will include (months 3,6,9,12):
 - a. Resource use questionnaire
 - b. 5-level EQ-5D^{32,33} (EQ-5D-5L, months 3,6,9,12 mean utility by study arm at each time point. Used to estimate QALYs as described in the HEAP).
- 6. Safety outcomes will include (continuous to 12 months):
 - a. AEs
 - b. AEs of special interest
- 7. Adherence and Tolerability
 - a. Visual Analog Scale (VAS)³⁴ for Medications Taken (VAS, months 3,6,9,12, mean scores)
 - b. Tolerability non validated measure Likert scale (months 3,6,9,12, mean scores and frequency distribution)

5 **PARTICIPANTS**

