9.2 DRDOCTOR

DrDoctor, a commercial web-based patient engagement platform, will facilitate the collection of patient reported outcome measures. Patient reported outcome measures will be collected in their validated format. Participants will be able to directly input data at the required time points (up to 1 week before each scheduled trial visit, except baseline where assessments will only be available that day). Site staff need to check that assessments have been completed at each study visit and request completion of any outstanding forms during the appointment. Study site staff experiencing issues with system access or functionality should contact a CI delegate (e.g Trial Manager). Patients experiencing issues with the system should contact the research team at the study site, who will seek advice from the CI delegate (e.g. Trial Manager).F

Participant's mobile number will be entered on to DrDoctor; the name, date of birth, post code, and hospital number entered onto DrDoctor are determined by 'patient tokens' that include no real participant data. No data will be entered onto the DrDoctor system unless a participant has signed a consent form to participate in the trial. To login into the staff portal, staff will be invited to create a username and account. Data entry will be automatically date and time stamped, alongside information about the user making the entry/changes within the system.

At the end of the trial, DrDoctor will provide a copy of the final exported dataset to the CI in .csv format and the CI will onward distribute as appropriate.

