9.6.2 DRDOCTOR

Data will be collected on the DrDoctor platform which will enable the system to collect longitudinal clinical data using PROMs – also known as electronic clinical outcome measures (eCOAs). The study site teams will undertake appropriate reviews of the data at each visit to ensure patient reported outcomes are completed. DrDoctor will provide the Trial Manager with a Data Management Plan for the system which will be filed in the Trial Master File. Data Management Reports will be downloaded by the Trial Manager.

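### The protocol specifies no review of the PHQ-9 self-harm item and no link from it to the adverse event log; site review of DrDoctor data is defined only as a completeness check.

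*Protocol*

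**What the plan says.** Protocol 6.4.2.6 presents the PHQ-9 as a nine-question patient-completed instrument, each question scored 0 to 3, whose content includes "concentration, speed of talking and moving and thoughts of self-harm or suicide". Self-harm and suicide are mentioned nowhere else in the protocol. Table 1 schedules the questionnaire at baseline, month 6 and month 12.

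On how it is completed, 6.4.2 says: "Participants should be informed to complete self report measures in the absence of any caregiver prior to each visit as instructed". Section 9.2 opens the forms a week ahead of each visit, except at baseline, where they are available only on the day.

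On what the site does with the answers, three statements matter:

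- 6.2.3, on access: "Site staff and monitors will be able to check if data has been entered and view the data only".
- 9.2, on the duty at the visit: "Site staff need to check that assessments have been completed at each study visit and request completion of any outstanding forms during the appointment".
- 9.6.2, on the purpose of review: "The study site teams will undertake appropriate reviews of the data at each visit to ensure patient reported outcomes are completed".

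On analysis, 4.2 reports PHQ-9 and GAD-7 at months 6 and 12 as "mean absolute change from baseline and proportion with score < 5".

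On safety, 6.5.3 has participants asked about AEs at each visit, and section 10 requires all AEs to be recorded from consent. Section 10.2 lists ocular surface disease, joint pain and facial rashes as events of special interest, with no mood event. Section 6.7 requires a physician to review and sign laboratory results and sends clinically significant abnormalities to the AE log.

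**The concern.** The trial asks a direct question about self-harm and stores the reply on a platform that site staff open at the visit. The stated reason for opening it is to see whether the form is there, not what it says. A site could follow the protocol exactly and still leave a disclosed suicidal thought unread.

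Two things are at stake. The first is participant safety: the disclosure is made privately, possibly days before the visit, and the protocol names no one to read it. The second is the completeness of the safety data. Appendix 2 lists depression (1.2.2) and altered mood and psychosis (1.2.3) among methotrexate side effects, and section 1.1 says that eczema itself harms mood. Comparative safety is a secondary objective (3.2). A new positive answer after baseline could sit in the questionnaire dataset and never be considered for the AE log.

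**Working it through.** The point rests on the text. The arithmetic shows only what the planned summaries can detect and gives a rough scale.

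**Step 1. Two data sources compared.**

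| | Laboratory results (6.7) | PHQ-9 self-harm item (6.4.2.6, 6.2.3, 9.2, 9.6.2) |
|---|---|---|
| Who must look at the content | A physician, who signs | No one named; staff can view |
| Stated purpose of review | Clinical review | Completeness |
| Route to the AE log | Yes, if clinically significant | None stated |

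The protocol builds this kind of route for one data source and not for the other.

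**Step 2. Ways a positive answer could still surface.** There are two. The participant may mention it at the AE enquiry (6.5.3), or a staff member who opens the form may notice it. Neither is triggered by the answer.

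**Step 3. Whether the planned outcome would show it.** The maximum total is 9 x 3 = 27. One item contributes 0 to 3 points, so a new positive answer raises the total by 1 to 3 points if the other answers are unchanged. The threshold summary can miss it altogether: a participant scoring 3 on the self-harm item and 1 elsewhere totals 4, below 5, and is counted in the favourable category. Neither summary in 4.2 isolates the item.

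**Step 4. Illustrative scale.** Inputs: 536 participants (synopsis); two post-baseline PHQ-9s (Table 1); 20% loss to follow-up at the primary endpoint (12.1), assumed here to apply at month 12 as well; a positive rate of 5% to 15%, which is an assumption.

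- Post-baseline forms due: 536 x 2 = 1,072
- Forms completed: 1,072 x 0.80 = 857.6, about 858
- Positive answers at 5%: 858 x 0.05 = 42.9, about 43
- Positive answers at 15%: 858 x 0.15 = 128.7, about 129

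These are answers, not participants, and not all would be new since baseline. Baseline forms are left out because they precede treatment and cannot show a drug harm, although the question of who reads the item applies to them too.

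**The case against.** The strongest reply is that this is silence and not error. Section 6.4.2.6 describes the instrument correctly and nothing contradicts it. Sections 9.5.2 and 9.6.2 send DrDoctor handling to a Data Management Plan, and 6.2.3 provides training on the platform. A procedure for positive answers may sit in one of those documents, which are not at hand. That possibility stands, so the claim must be limited to what the protocol specifies. It does not remove the point: the protocol refers to no such procedure, and where it does state the purpose of review it states completeness, twice.

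A reader might infer that a positive answer gets no clinical attention and no AE record. The documents do not support that. Staff can see the answers, participants are asked about AEs at each visit, and the baseline, month 6 and month 12 visits must be face to face (20.5). The AE definition in section 10 is wide enough to cover new suicidal thoughts once the site knows of them.

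A reader might also infer that a mood harm would be absent from the safety results. That too goes too far. Mood AEs are reportable once known, and PHQ-9 totals are compared at months 6 and 12. Tabulating the single item by arm is a matter that the SAP may properly hold.

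The objection that the positive rate is assumed also stands; the gap does not depend on it.

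**Conclusion.** The concern holds in a limited form. The protocol collects a self-harm item, defines site review of it only as a check for completeness, and specifies neither a reading of the item nor a link to the AE log. A positive answer can go unread, and a new one can be missing from the AE data, unless the participant speaks up or staff happen to notice.

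The figure of about 43 to 129 post-baseline positive answers is an illustration. It rests on an assumed 5% to 15% rate and on 80% completion at both follow-ups. The conclusion about the text needs neither assumption. It does rest on the protocol alone, and an operational document not at hand may already fill the gap.

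The primary analysis is unaffected. The sponsor should make the change because the gap concerns participant safety and is cheap to close.

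**What to change.** In 6.4.2.6, 9.2 and 9.6.2, extend the existing DrDoctor completeness check so that a named site role also reads the self-harm item, no later than that visit, and passes any positive answer to the investigator. State that answers which are new or worse than at baseline are assessed against the AE definition in section 10 for entry in the AE log. If an operational document already says this, a cross-reference is enough.

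The clinical response to a positive answer and its timing are for the sponsor and investigator to set. That includes whether answers given up to a week ahead should be looked at before the visit. A count of participants with a new positive item, by arm, at months 6 and 12 is optional and may sit in the SAP.

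The cost is a few sentences in the protocol, a short instruction to the 36 centres, and a little site time at three visits. No new visit or data collection is needed.
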